#### 10.4.5.1 Adverse Events

Treatment-emergent AEs, SAEs, deaths, AEs leading to study intervention discontinuation, will be summarized by the Medical Dictionary for Regulatory Activities (MedDRA) system organ class and preferred term.

#### 10.4.5.2 Vital Signs

Vital signs will be summarized as raw, change from baseline, including the maximum post-baseline value. Baseline values are defined as the last non-missing value prior to the first dose of study drug. The number and proportion of participants with vital sign abnormalities will be summarized at each scheduled visit.

# 10.4.5.3 Clinical Laboratory Tests

Laboratory parameters will be summarized as raw, change from baseline, including the maximum post-baseline value. Incidence of abnormal, high, or low values will be summarized. Shift tables will also be provided. Baseline values are defined as the last non-missing value prior to the first dose of study drug. The number and proportion of participants with clinical laboratory abnormalities will be summarized at each scheduled visit.

# 10.4.6 Other Analyses

Not applicable.

Clinical Protocol IM011237 BMS-986165 Deucravacitinib

# 10.5 Interim Analyses

Not applicable.

#### 10.6 Week 16 Primary Analysis

A 16-week primary analysis will occur once all randomized participants have completed their Week 16 visit or have discontinued prior to Week 16. Analyses of the collected efficacy and safety data will be performed. The study participants and investigators will remain blinded to the initial treatment assignment throughout the study. The Sponsor and site facing study team will be unblinded to the individual treatment assignments following the last Week 16 visit.

Additional details of these analyses will be described in the SAP. A final analysis will be performed after all participants complete the final safety follow-up visit at Week 56 or post-discontinuation follow-up visit.

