## 7.2 Method of Study Intervention Assignment

Before the study is initiated, each user (at investigative sites) will receive log-in information and directions on how to access the IRT system. At the time of the Screening Visit, immediately after informed consent is obtained and before any study-related procedures are performed, the investigative site will access the enrollment option of the IRT system for assignment of a participant number for all participants, including participants not subsequently randomized or treated. The participant number is assigned sequentially by the system and will be unique across all sites. All enrolled participants will be assigned sequential participant numbers. The participant number will not be used for any other participant. If a participant is rescreened, they will be given a new identification number.

At Day 1, participants who meet all criteria for enrollment at Screening and Day 1 will be centrally randomized in a 2:1 ratio to deucravacitinib 6 mg QD or placebo as determined by a computer-generated randomization schedule using IRT. The randomization lists will be generated by the IRT vendor using a permuted block design within each stratum level.

After all inclusion/exclusion criteria have been met for a participant, the investigative site will access the IRT on Day 1 for the purpose of randomizing a participant. An intervention group will be assigned by IRT based on the above-described randomization schedule. In addition, a unique kit number will be assigned to the participant corresponding to the intervention assignment.

Study intervention will be dispensed at study visits as shown in the Schedule of Activities (Section 2). When new intervention kits need to be provided, the investigative site will access the IRT to obtain the kit number to assign to the participant.

At Week 16, all participants, regardless of their blinded intervention, will be switched to open-label deucravacitinib 6 mg QD bottles through Week 52.

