#### 7.3.1 Maintaining the Blind

Blinded intervention assignments will be managed using IRT. IP supply will be controlled by IRT at each visit.

All tablets are identical in appearance and will be supplied in bottles with each daily dose made up of the appropriate combination of active and/or placebo tablets to provide the correct intervention, as shown in Table 7.1-1. Investigative site staff, Sponsor and designee personnel, and participants and their families will remain blinded to intervention assignments.

The Sponsor and site facing study team will be unblinded to the individual treatment assignments at the primary endpoint database lock after the last participant has completed the Week 16 visit.

Clinical Protocol BMS-986165

The primary analysis database lock will occur after all randomized participants completed their Week 16 visit or discontinued prior to Week 16. The study participants and investigators will remain blinded to the initial treatment assignment throughout the study.

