## 7.3.2 Circumstances for Unblinding

Blinding of study treatment assignment is critical to the integrity of this clinical study. However, in the event of a medical emergency or pregnancy in an individual participant in which knowledge of the IP is critical to the participant's management, the blind for that participant may be broken by the investigator. The participant's safety takes priority over any other considerations in determining if a treatment assignment should be unblinded.

Before breaking the blind of an individual participant's treatment, the investigator should determine that the unblinded information is necessary (ie, that it will alter the participant's immediate management). In many cases, particularly when the emergency is clearly not related to the IP, the problem may be properly managed by assuming that the participant is receiving the IP.

It is highly desirable that the decision to unblind treatment assignment be discussed with the Medical Monitor, but the investigator always has ultimate authority for the decision to unblind. The actual task of unblinding can be delegated by the investigator to a designee assigned the task on the Delegation of Authority. The Principal Investigator or appointed designee should only call in for emergency unblinding after the decision to unblind the participant has been documented.

For this study, the method of unblinding for emergency purposes is described in the IRT manual.

In case of an emergency, the investigator has unrestricted access to randomization information via IRT and is capable of breaking the blind through the IRT system without prior approval from the Sponsor. After the unblinding, the investigator shall notify the Medical Monitor or designee and/or study director. Participant and unblinded treatment information and the reason for the blind being broken must be recorded on the appropriate study status page of the eCRF. After unblinding via IRT, the investigator shall notify the Medical Monitor or designee.

In cases of accidental unblinding, contact the Medical Monitor and ensure every attempt is made to minimize additional disclosure and the impact of unblinding.

Any request to unblind a participant for nonemergency purposes should be discussed with the Medical Monitor.

If a participant is unblinded for any reason, the participant will be discontinued from treatment.

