#### 8 DISCONTINUATION CRITERIA

## 8.1 Discontinuation From Study Intervention

Participants MUST discontinue IP/IMP for any of the following reasons:

- Participant's request to stop study intervention. Participants who request to discontinue study intervention will remain in the study and must continue to be followed for protocol-specified follow-up procedures. The only exception to this is when a participant specifically withdraws consent for any further contact with him/her or persons previously authorized by the participant to provide this information
- Any clinical AE, laboratory abnormality, or intercurrent illness which, in the opinion of the investigator, indicates that continued participation in the study is not in the best interest of the participant
- Termination of the study by BMS
- Loss of ability to freely provide consent through imprisonment or involuntarily incarceration for treatment of either a psychiatric or physical (eg, infectious disease) illness.
  - Note: Under specific circumstances and only in countries where local regulations permit, a participant who has been imprisoned may be permitted to continue as a participant. Strict conditions apply, and BMS approval is required
- Abnormal liver tests suggestive of drug-induced liver injury (DILI), as defined in Section 9.2.8 or if the investigator believes that it is in the best interest of the participant
- The participant develops a malignancy, with the exception of a participant who develops non-melanoma skin cancer who may continue in the study at the discretion of the investigator
- Pregnancy, positive pregnancy test or participant expresses an interest in becoming pregnant (Section 9.2.6)
- Unblinding of a participant's intervention assignment for any reason (emergency or nonemergency)
- Inability or failure to comply with protocol requirements in the opinion of the investigator
- Participant reports suicidal ideation, suicidal behavior, or suicide attempts at any time after inclusion. The participant should then be immediately referred to a mental health professional for evaluation of suicide risk

Refer to the Schedule of Activities (Section 2) for data to be collected at the time of intervention discontinuation and follow-up and for any further evaluations that can be completed.

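### Does the planned Week 16 release of assignments to the Sponsor trigger the rule that unblinding ends a participant's treatment?

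*Combined protocol and SAP*

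**What the plan says.** Section 10.6 states that "The Sponsor and site facing study team will be unblinded to the individual treatment assignments following the last Week 16 visit". Section 7.3.1 names the same recipients and ties the moment to the lock: they are "unblinded to the individual treatment assignments at the primary endpoint database lock after the last participant has completed the Week 16 visit". Section 7.3.1 also says that "The study participants and investigators will remain blinded to the initial treatment assignment throughout the study", and Section 10.6 repeats this just before the sentence on release. Earlier in Section 7.3.1 a general sentence reads: "Investigative site staff, Sponsor and designee personnel, and participants and their families will remain blinded to intervention assignments".

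The stopping rule appears twice. The list in Section 8.1 opens with "Participants MUST discontinue IP/IMP for any of the following reasons", and one of its entries is "Unblinding of a participant's intervention assignment for any reason (emergency or nonemergency". Section 7.3.2, which sets out how a code may be broken, ends with "If a participant is unblinded for any reason, the participant will be discontinued from treatment".

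Section 7.2 sets the treatment after Week 16: "At Week 16, all participants, regardless of their blinded intervention, will be switched to open-label deucravacitinib 6 mg QD bottles through Week 52".

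**The concern.** The entry in Section 8.1 turns on the assignment becoming known and does not say to whom. Sections 7.3.1 and 10.6 then release every individual assignment to the Sponsor and to a site facing study team that the visible text does not define. Put together word for word, a planned administrative step meets a mandatory stopping criterion for everyone still on drug, against the plan to treat through Week 52.

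A second worry concerns Weeks 16 to 52. The current drug is then open-label and only the initial arm is still masked, yet disclosure of that arm to an investigator or participant would still end treatment. The site facing team holds that information, and the visible text does not say how it is kept from investigators.

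At stake would be on-treatment data after Week 16, which serve the reason that Section 5.4 gives for a 52-week study (maintenance of response), and consistent use of a mandatory rule across sites.

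**Working it through.** The protocol gives no figure to reproduce on this point. The check is a comparison of passages, followed by a calculation of scale.

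**1. What kind of unblinding the rule addresses.** Section 7.3.2 covers three routes: a medical emergency or pregnancy, with the code broken through the IRT; accidental unblinding; and a request for nonemergency reasons. Each concerns one participant. The discontinuation sentence closes that section and takes the individual participant as its subject. The parenthesis in Section 8.1 repeats the same division into emergency and nonemergency. Release of the whole list to Sponsor staff for the primary analysis is none of these routes.

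**2. Who learns what at the lock.** Participants and investigators stay blinded to the initial arm (Sections 7.3.1 and 10.6). The people who would apply Section 8.1 at the site therefore receive no assignment through the planned release.

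**3. What the rest of the protocol assumes.** Treatment of all participants through Week 52 is stated in the Protocol Summary (Overall Design, Intervention Groups and Duration, Brief Summary) and in Sections 5.1.3 and 7.2. Section 10.6 places the final analysis after the Week 56 visit or the post-discontinuation visit. A reading that stops treatment at the lock contradicts all of these.

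**4. Timing.** Section 7.3.1 places the lock after the last Week 16 visit, and Section 10.6 says the release follows that visit. The two agree, so no Week 16 assessment is made after the release. Every hypothesis in Section 10.1 concerns Week 16.

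**5. Scale of the word-for-word reading.** Inputs from the protocol: 174 randomized (Section 5.2) and 52 − 16 = 36 open-label weeks, so 174 × 36 = 6264 planned person-weeks. Assumed, because the protocol gives neither: A weeks of uniform accrual, L weeks from the last Week 16 visit to lock, and no dropout.

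- Still on treatment at lock = 174 × min(1, (36 − L)/A).
- Person-weeks after lock = 174 × ((36 − L) − A/2) if A ≤ 36 − L; otherwise 174 × (36 − L)²/(2A).

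| L | A | On treatment at lock | Person-weeks after lock |
|---|---|---|---|
| 4 | 26 | 174 | 174 × (32 − 13) = 3306 (53%) |
| 8 | 26 | 174 | 174 × (28 − 13) = 2610 (42%) |
| 8 | 52 | 174 × 28/52 = 94 | 174 × 784/104 = 1312 (21%) |
| 8 | 104 | 174 × 28/104 = 47 | 174 × 784/208 = 656 (10%) |
| 12 | 104 | 174 × 24/104 = 40 | 174 × 576/208 = 482 (8%) |

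These figures describe only the word-for-word reading. On the reading in steps 1 to 3, the planned release stops no one. The number of individual disclosures during Weeks 16 to 52 cannot be estimated from the protocol.

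**The case for a change.** The strongest reply is that a mandatory stopping rule should not depend on inference. Section 8.1 names the assignment and not the recipient, applies to any cause, and has no limit by period or by planned event. The narrower scope is nowhere written, and a site could in principle apply the rule differently from its neighbour. That much stands: the scope is unstated.

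The second worry carries less. The protocol keeps participants and investigators blind to the initial arm until the end of the study, so a rule that still applies to a break of that blind after Week 16 agrees with the rest of the text. Whether it is a good stopping rule is a clinical matter on which this review takes no position. Section 7.3.2 also asks the investigator to confirm, before breaking the code, that the information would alter immediate management, which limits deliberate breaks once the current drug is known. If a participant is stopped, Section 8.1.2 requires outcome follow-up to the end of the study. On-treatment status is lost, but collection of Week 52 outcomes is still required.

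The remaining items are drafting. A general statement that Sponsor staff remain blinded, followed by a specific planned exception, is ordinary construction. Arrangements for the site facing team may sit in the monitoring plan cited in Appendix 2 or in redacted text, so their absence here shows little.

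**Conclusion.** The concern identifies a real gap in wording but not a conflict between two intended rules. Sections 7.3.2 and 8.1 do not say whether they cover the planned release; their context points to individual code breaks, and the masking and treatment provisions elsewhere fit only that reading. Under it the release ends treatment for nobody. The 40 to 174 participants and 482 to 3306 person-weeks belong to a reading that the protocol's other provisions exclude, and they rest on assumed accrual, lock lag and no dropout, so they do not measure practical impact.

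The Week 16 confirmatory results are the same on either reading, because the release follows the last Week 16 visit. A sponsor following the plan sensibly would also obtain the same Week 52 data with or without an explicit scope clause. The exact scope of the discontinuation rule is for the sponsor to state. Nothing in the statistical plan needs to change.

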# 12 APPENDICES

# APPENDIX 1 ABBREVIATIONS AND TRADEMARKS

Term	Definition
AE	adverse event
ALT	alanine aminotransferase
ANCOVA	analysis of covariance
anti-HBc	hepatitis B core antibody
anti-HBc total	hepatitis B core antibody total
anti-HBs	hepatitis B surface antibody
AST	aspartate aminotransferase
AxMP	auxiliary medicinal product
BID	twice daily
BMI	body mass index
BMS	Bristol-Myers Squibb Company
BP	blood pressure
BSA	body surface area
CFR	Code of Federal Regulations
CI	confidence interval
CMH	Cochran-Mantel-Haenszel
COVID-19	coronavirus disease 2019
CRF	Case Report Form
CSR	clinical study report
CTAg	Clinical Trial Agreement
CYP450	cytochrome P450
DILI	drug-induced liver injury
DLQI	Dermatology Life Quality Index
DNA	deoxyribonucleic acid
ECG	electrocardiogram
eCRF	electronic case report form
EDC	electronic data capture
e-diary	electronic diary
ЕОТ	end of treatment
ET	early termination
EU	European Union
FAS	Full Analysis Set
FDA	Food and Drug Administration

Term	Definition
FSH	follicle-stimulating hormone
GCP	Good Clinical Practice
GIC-SI	Global Impression of Change-Scalp Itch
	Green impression of enumge 2000 1001
HBsAg	hepatitis B surface antigen
HBV	hepatitis B virus
hCG	human chorionic gonadotropin
HCV	hepatitis C virus
HIPAA	Health Insurance Portability and Accountability Act
HIV	human immunodeficiency virus
HRQoL	health-related quality of life
HRT	hormone replacement therapy
IB	Investigator's Brochure
ICE	intercurrent events
ICF	informed consent form
ICH	International Council for Harmonisation
ICMJE	International Committee of Medical Journal Editors
IEC	Independent Ethics Committee
IFN	interferon
IL	interleukin
IMP	investigational medicinal product
IP	investigational product
IRT	interactive response technology
I-s-PGA	Intertriginous-area static Physician Global Assessment
IUS	intrauterine hormone-releasing system
JAK	Janus kinase
LAM	lactational amenorrhea method
MCT	meaningful change threshold
M. IDD A	M 1' 1D' (' C D 1 ( A (' '')
MedDRA	Medical Dictionary for Regulatory Activities
n/a	not applicable
NIMD	non investigational are disingle and their
NIMP	non-investigational medicinal product
NDI	non noon on don invarytetien
NRI	non-responder imputation

Term	Definition
NRS	Numerical Rating Scale
PASI	Psoriasis Area and Severity Index
17151	1 Sofiasis Area and Severity index
PBO	placebo
TBO	piaceoo
PE	physical examination
PGA-F	Physician Global Assessment-Fingernails
PGA-G	Physician Global Assessment-Genitals  Physician Global Assessment-Genitals
TOA-O	Filysician Global Assessment-Genitals
	<del> </del>
DV	who were a live time.
PK	pharmacokinetics
PC 4	1 1 4 1 1 1 1 1 1 1 1 1 1 1 1 1 1 1 1 1
pp-PGA	palmoplantar Physician Global Assessment
PRO	patient-reported outcome
DCO	
PSO	psoriasis
OD	1 '1
QD	once daily
QoL SAE	quality of life serious adverse event
SAP	
SARS-CoV-2	statistical analysis plan severe acute respiratory syndrome coronavirus 2
SARS-COV-2	severe acute respiratory syndrome coronavirus 2
af DC A	static force Physician Clobal Accessment
sf-PGA	static face Physician Global Assessment static Physician Global Assessment
s-PGA	
s-PGA-G	static Physician Global Assessment Genitalia
SSC	Study Steering Committee
ss-PGA	scalp-specific Physician Global Assessment
STAT	signal transducer and activator of transcription
TD	
TB	tuberculosis
TNF	tumor necrosis factor
TSQM	Treatment Satisfaction Questionnaire for Medication
TYK2	tyrosine kinase 2
LILA	1: '. 6 1
ULN	upper limit of normal
US	United States
UV	ultraviolet

Term	Definition
WOCBP	women of childbearing potential

#### APPENDIX 2 STUDY GOVERNANCE CONSIDERATIONS

The terms "participant" and "subject" refer to a person who has consented to participate in the clinical research study. Typically, the term "participant" is used in the protocol and the term "subject" is used in the Case Report Form (CRF).

#### **REGULATORY AND ETHICAL CONSIDERATIONS**

This study will be conducted in accordance with:

- Consensus ethical principles derived from international guidelines, including the Declaration of Helsinki and Council for International Organizations of Medical Sciences International Ethical Guidelines
- Applicable International Council for Harmonisation (ICH) Good Clinical Practice (GCP) Guidelines
- Applicable laws, regulations, and requirements

The study will be conducted in compliance with the protocol. The protocol, any revisions/amendments, and the participant informed consent form (ICF) will receive approval/favorable opinion by Institutional Review Board/Independent Ethics Committee (IRB/IEC), and regulatory authorities according to applicable regulations prior to initiation of the study.

All potential serious breaches must be reported to the Sponsor or designee immediately. A potential serious breach is defined as a Quality Issue (eg, protocol deviation) that is likely to affect, to a significant degree, one or more of the following: (1) the rights, physical safety or mental integrity of 1 or more participants; (2) the scientific value of the clinical study (eg, reliability and robustness of generated data). Items (1) or (2) can be associated with either GCP regulation(s) or study protocol(s).

Personnel involved in conducting this study will be qualified by education, training, and experience to perform their respective tasks.

This study will not use the services of study personnel where sanctions have been invoked or where there has been scientific misconduct or fraud (eg, loss of medical licensure, debarment).

#### INSTITUTIONAL REVIEW BOARD/INDEPENDENT ETHICS COMMITTEE

Before study initiation, the investigator must have written and dated approval/favorable opinion from the IRB/IEC for the protocol, Investigator's Brochure, product labeling information, ICF, participant recruitment materials (eg, advertisements), and any other written information to be provided to participants.

The investigator, Sponsor, or designee should provide the IRB/IEC with reports, updates, and other information (eg, expedited safety reports, amendments, administrative letters) annually, or more frequently, in accordance with regulatory requirements or institution procedures.

Protocol Amendment 02 Date: 25-May-2023 IM011237 Deucravacitinib The investigator is responsible for providing oversight of the conduct of the study at the site and adherence to requirements of the following where applicable:

- ICH guidelines,
- United States Code of Federal Regulations, Title 21, Part 50 (21 CFR 50)
- European Union Directive 2001/20/EC; or
- European Regulation 536/2014 for clinical studies (if applicable),
- European Medical Device Regulation 2017/745 for clinical device research (if applicable),
- the IRB/IEC
- and all other applicable local regulations.

